5.7.3. Analysis of Exploratory Vaccine Response Variables

Exploratory vaccine response variables will be analyzed in a similar manner as described for the secondary vaccine response variables.

Accompanying descriptive analyses will be provided to all (primary/secondary/exploratory) vaccine response variables.

The distribution of endpoint variables will be checked to ensure ANCOVA type analyses are appropriate. If such modeling is deemed not appropriate, only raw data descriptions will be provided.

On limited numbers of samples, an exploratory analysis will be performed with data from a second neutralization assay that will be summarized in a separate report.

5.7.4. Analysis of Additional Vaccine Response Variables

VNT and WHO standard units will be analyzed in a similar manner as described for the primary vaccine response variable. Efficacy variables may also be explored using the mFAS.

5.7.5. Supplementary and Subgroup Analyses

Supplementary analysis:

In order to assess the consistency of results due to concurrent randomization, analyses of the primary vaccine response variable may be performed separately within waves 1, 2 and within waves 3, 4, respectively.

Subgroup analysis:

The following subgroup analysis may be performed in Per Protocol Analysis Set in order to assess the consistency of results:

- age groups: <65 vs ≥ 65 (if applicable)
- gender: male vs female

5.7.6. Analysis of sub-study vaccine booster administration

Analysis to include assessment of vaccine immune responses over time among the vaccine booster analysis set. Accompanying descriptive statistics at individual time points will also be provided.

5.8. Analysis of Safety Data

The analysis of safety and tolerability will be performed within the SAF population.

5.8.1. Adverse Events

All AEs reported in this study will be coded using the currently available version of MedDRA®. Coding will be to lowest level terms. The PT and the primary SOC will be listed.

All adverse events will be provided in a listing. Listing of deaths and other SAEs will also be provided.

Tabulations by treatment group will include the following:

All periods combined

- Overview of TEAEs
- TEAEs by SOC and PT
- TEAEs by SOC and PT and Severity
- Serious TEAEs by SOC and PT
- Study Drug Related TEAEs by SOC and PT
- Vaccine Related TEAEs by SOC and PT
- Study Drug Related Infusion Related Reaction TEAEs by SOC and PT

- Study Drug Related Injection Site Reaction TEAEs by SOC and PT
- Vaccine Related Injection Site Reaction TEAEs by SOC and PT
- Study Drug Related Hypersensitivity Reaction TEAEs by SOC and PT
- Vaccine Related Hypersensitivity Reaction TEAEs by SOC and PT
- Treatment-Emergent AESIs by SOC and PT
- TEAEs leading to permanent discontinuation of vaccine by SOC and PT
- TEAEs leading to permanent discontinuation of study drug by SOC and PT
- TEAEs leading to death by SOC and PT

Pre-vaccination period

- Overview of TEAEs
- TEAEs by SOC and PT
- TEAEs by SOC and PT and Severity
- Serious TEAEs by SOC and PT
- Study Drug Related TEAEs by SOC and PT
- Study Drug Related Infusion Related Reaction TEAEs by SOC and PT
- Study Drug Related Injection Site Reaction TEAEs by SOC and PT
- Study Drug Related Hypersensitivity Reaction TEAEs by SOC and PT
- TEAEs leading to permanent discontinuation of study drug by SOC and PT
- TEAEs leading to death by SOC and PT

Primary series vaccination period and Post-booster vaccination period

- Overview of TEAEs
- TEAEs by SOC and PT
- TEAEs by SOC and PT and Severity
- Serious TEAEs by SOC and PT
- Study Drug Related TEAEs by SOC and PT
- Vaccine Related TEAEs by SOC and PT
- Study Drug Related Infusion Related Reaction TEAEs by SOC and PT
- Study Drug Related Injection Site Reaction TEAEs by SOC and PT
- Vaccine Related Injection Site Reaction TEAEs by SOC and PT
- Study Drug Related Hypersensitivity Reaction TEAEs by SOC and PT
- Vaccine Related Hypersensitivity Reaction TEAEs by SOC and PT

- TEAEs leading to permanent discontinuation of vaccine by SOC and PT
- TEAEs leading to permanent discontinuation of study drug by SOC and PT
- TEAEs leading to death by SOC and PT

5.8.2. Clinical Laboratory Measurements

Laboratory test results will be tabulated by baseline and change from baseline to each scheduled assessment time with descriptive statistics.

Number and percentage of subjects with potentially clinically significant value (PCSV) at any post-randomization time point will be tabulated for each clinical laboratory test for all subjects and separately for subjects in whom the PCSV criterion was normal or missing at baseline.

Shift tables based on baseline normal/abnormal and other tabular and graphical methods may be used to present the results for laboratory tests of interest.

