9.1.1. Footnotes for the Schedules of Events

1. Throughout the study, study drug and/or vaccine administration will occur after all samples have been collected and all assessments have been performed.
2. Separate consent is required for participation in the optional vaccine booster sub-study (Section 9.2.10), optional future biomedical research sub-study (Section 9.2.8), and optional pharmacogenomics sub-study (Section 9.2.9). For subjects consenting to the genomics sub-study, the blood sample for genomic DNA should be collected at baseline (day 1) but may be collected at any visit.
3. All women of childbearing potential (WOCBP), with the exception of women with documented bilateral tubal ligation, will require pregnancy testing at screening, prior to study drug administration, and prior to COVID-19 vaccine administration. If a urine pregnancy test result is positive, a serum pregnancy test will be performed for confirmation. Subjects with confirmed pregnancy (by serum test) at screening will not be randomized. If the screening visit occurs on the same day as the baseline visit on day 1, pregnancy testing does not need to be repeated. Subjects with confirmed pregnancy at post-baseline dosing visits will be counseled according to Section 8.3.3.
4. If the screening visit occurs on the same day as the baseline visit on day 1, SARS-CoV-2-rapid RT-PCR test does not need to be repeated. Nasopharyngeal swabs will be used for rapid RT-PCR testing. Refer to Section 6.1.2 for more information on sample collection and visit scheduling for subjects with suspected COVID-19 or positive RT-PCR test result.

Post-baseline samples only: If the rapid RT-PCR test is positive at any time point post-baseline, the samples will be banked for viral sequencing.

Additional information is provided in Section 9.2.1.2.

5. If a rapid serology test is used at the screening visit, and screening occurs on the same day as the baseline visit, the rapid serology test does not need to be repeated at baseline. Additional information about the rapid serology test is provided in Section 9.2.1.3.

At screening, if the rapid serology test is not available locally, a rapid test may be performed at a central laboratory to determine eligibility, and a repeat of the test is not required at baseline.

6. Subjects will receive site-managed assignment (at screening) and randomized treatment assignment (at baseline on day 1) according to Section 8.5.

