2. INVESTIGATION PLAN

2.1. Study Design and Randomization

This study is a phase 2, randomized, open-label, parallel group study in healthy adult volunteers to assess the immunogenicity, safety, and tolerability of Moderna mRNA-1273 vaccine when administered with REGN10933+REGN10987.

At screening, eligible subjects were to be assigned to an enrollment wave. The enrollment waves were intended to avoid or minimize the potential for unused doses of Moderna mRNA-1273 COVID-19 vaccine (Protocol Section 3.2.1 for additional rationale). Every effort was made by sites to avoid unused doses of vaccine.

Every effort was made by the site to ensure balance of age (<65 years and \geq 65 years) within each of the enrollment waves. At baseline (day 1), subjects were to be randomized to the corresponding study arms in each wave as described in [Table 1](#).

Randomization was performed according to a computer-generated randomization scheme provided by an interactive web response system (IWRS) to a designated study pharmacist or a qualified designee.

Randomization was stratified by age (<65 years versus \geq 65 years).

Table 1: Study Treatment Assignment

Study Arm	Randomization Ratio	Targeted Enrollment	Co-administered REGN10933+REGN10987 Combination Therapy	Moderna mRNA-1273 Vaccine*
Enrollment Wave 1				
1	2	30	1200 mg (600 mg of each mAb) IV on day 1	On day 15 and day 43
2	2	30	300 mg (150 mg of each mAb) IV on day 1	On day 15 and day 43
3	2	30	150 mg (75 mg of each mAb) IV on day 1	On day 15 and day 43
6a	1	15	None	On day 15 and day 43
Enrollment Wave 2				
4	2	30	1200 mg (600 mg of each mAb) SC on day 1	On day 1 and day 29
5	2	30	600 mg (300 mg of each mAb) SC on day 1	On day 1 and day 29
6b	1	15	None	On day 1 and day 29
Enrollment Wave 3				
7	15	30	48 mg (24 mg of each mAb) IV on day 1	On day 15 and day 43
8	15	30	12 mg (6 mg of each mAb) IV on day 1	On day 15 and day 43
6c	4	8	None	On day 15 and day 43
Enrollment Wave 4				
9	15	30	1200 mg (600 mg of each mAb) IV on day 7	On day 1 and day 29

6d	4	8	None	On day 1 and day 29
----	---	---	------	---------------------

*Moderna mRNA-1273 vaccine will be administered as described on the US FDA EUA HCP Fact Sheet, 2021)
mAb=monoclonal antibody; SC=subcutaneous; IV=intravenous.

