6.1. Definition of Baseline

Unless otherwise specified, the baseline assessment for all measurements will be the latest available valid measurement taken prior to the administration of the first dose of Moderna mRNA-1273 vaccine or REGN10933+REGN10987 (as applicable and whichever occurs first).

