Drug concentrations and Immunogenicity																	
Drug concentration (PK) sample ¹⁰						X ¹⁰		X ¹⁰	X	X	X	X	X	X			
Immunogenicity (ADA) sample ¹¹						X ¹¹											
Pharmacogenomics (Optional)																	
Whole Blood for DNA			X ²														
Vaccine Booster Sub-Study (Optional)¹⁴																	
Visit Period	Screening/Baseline			Vaccine Response Assessment			Follow-Up					Unscheduled Visit	ET				
Study Day	Screening	Pre-dose	Dose ¹	Post-Dose	Pre-dose	Dose ¹	Post-Dose	15	29 ¹	43	57	169	253	366			
Days After the First Vaccine Dose								14	28	42	56	168	252	365			
Window (day)								±2	±1 to +3	±2	±2	±7	±14	±14			
Informed consent for vaccine booster sub-study ²								Refer to Table 6.									
Sample collection and assessments																	

Table 5: Schedule of Events for the Moderna mRNA-1273 Vaccine Booster Sub-Study

Visit	Vaccine Booster Administration			Post-Booster Follow-Up
	Pre-Dose	Dose ¹	Post-Dose	
Visit Window	≥5 months after the second dose of the vaccine (primary series), and >35 days before end of the main study		28 days ±7 days after the vaccine booster	
Informed consent for the booster sub-study ²	X			
Moderna mRNA-1273 vaccine booster shot		X		
Pregnancy test (WOCBP) ³	X			
SARS-CoV-2 rapid (local/POC) RT-PCR ⁴	X ⁴			X ⁴
Adverse events ¹²	X	X	X	X
Drug concentration (PK) sample ¹⁰	X			X
Serum for exploratory research	X			X
Plasma for exploratory research	X			X
Whole blood for PBMCs ⁸	X			X

Footnotes for the Schedules of Events:

1. Throughout the study, study drug and/or vaccine administration will occur after all samples have been collected and all assessments have been performed.
2. Separate consent is required for participation in the optional vaccine booster sub-study (Protocol Section 9.2.10), optional future biomedical research sub-study (Protocol Section 9.2.8), and optional pharmacogenomics sub-study (Protocol Section 9.2.9). For subjects consenting to the genomics sub-study, the blood sample for genomic DNA should be collected at baseline (day 1) but may be collected at any visit.

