WBC	<3.0 Giga/L or $<$ LLN (if LLN ≤ 3.0 Giga/L) and baseline ≥ 3.0 Giga/L or \geq LLN (if LLN ≤ 3.0 Giga/L) (Non-Black); <2.0 Giga/L or $<$ LLN (if LLN ≤ 2.0 Giga/L) and baseline ≥ 2.0 Giga/L or \geq LLN (if LLN ≤ 2.0 Giga/L) (Black) ≥ 16.0 Giga/L or \geq ULN (if ULN ≥ 16.0 Giga/L) and baseline < 16 Giga/L or $<$ ULN (if ULN ≥ 16.0 Giga/L)	Increase in WBC: not relevant.
Lymphocytes	>4.0 Giga/L or $>$ ULN (if ULN ≥ 4.0 Giga/L) and baseline ≤ 4.0 Giga/L or \leq ULN (if ULN ≥ 4.0 Giga/L)	
Neutrophils	<1.5 Giga/L or $<$ LLN (if LLN ≤ 1.5 Giga/L) and baseline ≥ 1.5 Giga/L or \geq LLN (if LLN ≤ 1.5 Giga/L) (Non-Black); <1.0 Giga/L or $<$ LLN (if LLN ≤ 1.0 Giga/L) and baseline ≥ 1.0 Giga/L or \geq LLN (if LLN ≤ 1.0 Giga/L) (Black)	International Consensus meeting on drug-induced blood cytopenias, 1991.

Parameter	PCSV For Studies in healthy subjects only	Comments
Monocytes	>0.7 Giga/L or >ULN (if $ULN \geq 0.7$ Giga/L) and baseline ≤ 0.7 Giga/L or \leq ULN (if $ULN \geq 0.7$ Giga/L)	
Basophils	>0.1 Giga/L or >ULN (if $ULN \geq 0.1$ Giga/L) and baseline ≤ 0.1 Giga/L or \leq ULN (if $ULN \geq 0.1$ Giga/L)	
Eosinophils	>0.5 Giga/L or >ULN (if $ULN \geq 0.5$ Giga/L) and baseline ≤ 0.5 Giga/L or \leq ULN (if $ULN \geq 0.5$ Giga/L)	Harrison- Principles of Internal Medicine 17 th Ed., 2008.
Hemoglobin	
≤ 115 g/L or \leqLLN (if $LLN \leq 115$ g/L) and baseline > 115 g/L or $>$LLN (if $LLN \leq 115$ g/L) for male; ≤ 95 g/L or \leqLLN (if $LLN \leq 95$ g/L) and baseline > 95 g/L or $>$LLN (if $LLN \leq 95$ g/L) for Female.
 
≥ 185 g/L or \geqULN (if $ULN \geq 185$ g/L) and baseline < 185 g/L or $<$ULN (if $ULN \geq 185$ g/L) for Male; ≥ 165 g/L or \geqULN (if $ULN \geq 165$ g/L) and baseline < 165 g/L or $<$ULN (if $ULN \geq 165$ g/L) for Female
 
Decrease from Baseline ≥ 20 g/L
	Three criteria are independent.
Hematocrit	
≤ 0.37 v/v or \leqLLN (if $LLN \leq 0.37$ v/v) and baseline > 0.37 v/v or $>$LLN (if $LLN \leq 0.37$ v/v) for Male; ≤ 0.32 v/v or \leqLLN (if $LLN \leq 0.32$ v/v) and baseline > 0.32 v/v or $>$LLN (if $LLN \leq 0.32$ v/v) for Female
 
≥ 0.55 v/v or \geqULN (if $ULN \geq 0.55$ v/v) and baseline < 0.55 v/v or $<$ULN (if $ULN \geq 0.55$ v/v) for Male; ≥ 0.5 v/v or \geqULN (if $ULN \geq 0.5$ v/v) and baseline < 0.5 v/v or $<$ULN (if $ULN \geq 0.5$ v/v) for Female
	Two Criteria are independent
RBC	≥ 6 Tera/L or \geq ULN (if $ULN \geq 6$ Tera/L) and baseline < 6 Tera/L or $<$ ULN (if $ULN \geq 6$ Tera/L)	

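### In waves 1 and 3 the SAP's laboratory baseline is day 1 in the drug arms but day 15 in controls 6a and 6c, so the one post-infusion, pre-vaccine laboratory visit has no control comparison

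*SAP*

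**What the plan says.** SAP 6.1 defines baseline, unless otherwise specified, as "the latest available valid measurement taken prior to the administration of the first dose of Moderna mRNA-1273 vaccine or REGN10933+REGN10987", whichever occurs first. SAP 5.1 repeats the rule. SAP 5.7 sets a different baseline, but only for the vaccine-response variables.

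SAP 2.1, Table 1, shows when each arm first receives a product. Arm 1 is "1200 mg (600 mg of each mAb) IV on day 1", and arms 2, 3, 7 and 8 also receive study drug on day 1. The row for control 6a reads "6a 1 15 None On day 15 and day 43"; 6c has the same vaccine days. Randomization is on day 1 in every arm. Footnote 1 to the schedules, in both documents, fixes the order within a visit: "study drug and/or vaccine administration will occur after all samples have been collected and all assessments have been performed".

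SAP 5.8.2 plans summaries of change from baseline at each scheduled time. For PCSVs it says: "Number and percentage of subjects with potentially clinically significant value (PCSV) at any post-randomization time point will be tabulated". It asks for that count in all subjects and again in subjects whose criterion was normal or missing at baseline. Shift tables are optional.

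Each laboratory criterion in SAP Appendix 11.2 either carries a condition on the baseline value or is itself a change from baseline, such as the hemoglobin criterion "Decrease from Baseline ≥ 20 g/L".

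**The concern.** The counting window in SAP 5.8.2 opens at randomization, which is day 1 for everyone. The baseline rule in SAP 6.1 opens at first product, which is day 1 in the drug arms and day 15 in 6a and 6c. For those controls one post-randomization visit is both inside the counting window and the reference against which it is judged. The SAP does not resolve this.

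Two things are at stake. First, the drug arms get one more opportunity than their randomised controls to show a change or a new PCSV. Second, day 15 is the only scheduled laboratory visit in these waves after the infusion and before any vaccine, so it isolates the antibody. The controls have both day-1 and day-15 samples, which would give the concurrent 14-day change without drug, but the baseline rule leaves their day-1 sample unused.

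**Working it through.** The documents state no number of laboratory looks, so there is no planned figure to reproduce.

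**Inputs**
- Chemistry and hematology in waves 1 and 3: before dosing on day 1, then days 15, 43, 71 and 183, on one schedule for drug and control arms (Protocol Table 3, SAP Table 2).
- First product: day 1 in arms 1, 2, 3, 7 and 8; day 15 in 6a and 6c.
- Planned numbers: 5 × 30 = 150 drug-arm subjects; 15 + 8 = 23 controls.

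**Step 1. Apply the SAP 6.1 rule**

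| | Drug arms 1, 2, 3, 7, 8 | Controls 6a, 6c |
|---|---|---|
| Baseline | day 1 | day 15, before vaccine |
| Scheduled post-baseline looks | 15, 43, 71, 183 (4) | 43, 71, 183 (3) |
| Interval for day-43 change | 43 − 1 = 42 days | 43 − 15 = 28 days |

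**Step 2. Compare a control's day-15 value with itself.** The change is zero. A criterion that needs a value beyond a threshold and a baseline on the normal side of it cannot be met when the two are the same number. Neither can a 20 g/L fall or a 30% change. A check of banded, single-threshold, absolute-change and percentage-change forms over 200,000 random values with value equal to baseline found no case that qualified.

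**Step 3. Illustrate the size.** Assume no drug effect, the same per-look PCSV rate p in both groups, and independent looks. Then P(at least one) = 1 − (1 − p)^k, with k = 4 or 3.

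| Assumed p | Drug arms, k = 4 | Controls, k = 3 | Ratio |
|---|---|---|---|
| 1% | 3.9% | 3.0% | 1.33 |
| 2% | 7.8% | 5.9% | 1.32 |
| 5% | 18.5% | 14.3% | 1.30 |
| 10% | 34.4% | 27.1% | 1.27 |

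The per-look rates are assumptions; the documents give none. As p approaches zero the ratio tends to 4/3. For exchangeable looks 4/3 is also the ceiling whatever the correlation: a subject with any PCSV among four looks still has one in at least three of the four possible sets of three. Positive within-subject correlation pulls the ratio down, to 1 if a subject's looks all agree.

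**Step 4. Absolute terms.** At p = 1% the gap is 3.94 − 2.97 = 0.97 points, or 0.0097 × 23 = 0.2 of a control. At p = 2% it is 7.76 − 5.88 = 1.88 points, or 0.4 of a control. The standard error of a 5.9% proportion in 23 subjects is √(0.059 × 0.941 / 23), about 5 points.

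**The case against.** The strongest case on the other side has five parts.

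*Two PCSV tables are planned.* A reader might infer that no control can be counted at day 15 in any table. The documents do not settle that. If every PCSV already needs a normal baseline, the second count in SAP 5.8.2 largely repeats the first, so the all-subjects count may be meant as thresholds alone. On that reading day 15 counts in every arm and that table is unaffected for threshold criteria. Appendix 11.2 as written points the other way, and the normal-or-missing-at-baseline count and the change table are affected on either reading. A very literal reading of the clauses that offer a normal limit as an alternative threshold could also flag a value against itself (creatinine 160 μmol/L with an upper limit of 170, say), but that looks unintended.

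*The convention is coherent.* Baseline before first product matches the treatment-emergent definition in SAP 4.6.1, and controls have no pre-vaccination period there. This explains the rule, but it does not restore the day-15 comparison.

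*Shift tables.* A reader might infer that these are inflated too. SAP 5.8.2 makes them optional and does not say whether they are by visit or by worst value. A by-visit table is not inflated by an extra visit.

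*Other samples.* Unscheduled values (SAP 6.5) and early-termination samples can add looks in any arm, so four against three counts scheduled looks only. They do not give back the lost control visit.

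*Importance.* Protocol 11.1 plans no hypothesis tests, and the listed safety endpoints are based on adverse events. This stands and limits the weight of the point.

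**Conclusion.** The point holds for scheduled chemistry and hematology in waves 1 and 3. Post-baseline looks are four in the drug arms and three in 6a and 6c, control change at day 15 is zero by construction, and the day-43 change covers 42 days in one group and 28 in the other. These facts need no assumed rate. Losing the concurrent control at day 15 matters more than the extra look.

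The direction of the PCSV bias is upward in the drug arms when there is no drug effect. A ratio near 1.3 should not be read as the expected size: it rests on independent looks at unsourced rates and lies close to the 4/3 ceiling. With 23 controls the excess is well inside sampling error at the lower rates.

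The effect is confined to descriptive safety tables. Waves 2 and 4 are not affected, because drug and control arms there share a day-1 baseline. Urinalysis has no day-15 sample. Nothing here touches the primary analysis or a listed secondary endpoint.

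**What to change.** Add one sentence to SAP 5.8.2, with a matching exception in 6.1: in waves 1 and 3 the laboratory baseline is the day-1 pre-dose sample in every arm, including 6a and 6c. Day 15 then becomes a post-baseline visit in all arms. Scheduled looks are four against four and the change intervals match. Compare within wave: arms 1, 2 and 3 with 6a; arms 7 and 8 with 6c. The same edit should say whether the all-subjects PCSV count applies the baseline conditions of Appendix 11.2.

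The cost is a derivation flag; the samples are already scheduled. The downside is that the 6a and 6c baseline then falls 14 days before vaccine, whereas in 6b and 6d it is on the day of vaccination. SAP 5.7.1 pools the vaccine-alone arms; it sits in the vaccine-response section, so whether it governs safety tables is open. Under the present rule 6a and 6c line up with 6b, which has three looks at 28, 56 and 168 days after first vaccine. After the change they would not, so any safety table that pools controls across waves should footnote the different baseline offset and number of looks.
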